3 FLOWCHART OF THE STUDY

Study 990 Part I and II		Visit	V1	V2	V3	V4	V5	V6	V7	V8	V9	V10	V11	V12	V13	V14	
Assessments	Phase	Screening	Baseline	Treatment												EoT	Follow-up
Informed consent		•	• ^c														
Medical history incl. previous/current medication, vaccination status, risk factors, and demography			•														
Eligibility criteria (inclusion / exclusion)		•															
Safety Assessments																	
Adverse events		•	•	•	•	•	•	•	•	•	•	•	•	•	•	•	
Physical examination (full at screening and baseline and targeted afterwards)			•	•	•	•	•	•	•	•	•	•	•	•	•	•	
Vital signs (pulse, blood pressure, temperature)		•	•	•	•	•	•	•	•	•	•	•	•	•	•	•	
ECG (12 lead)		•															
Body weight and height (at screening only)		•											•				
Safety laboratory ^e		• ^f	• ^f			•	•	•	•	•	•	•	•	•	•	•	
Auto-antibodies (ANA, anti-dsDNA, thyroid gland [TPO, TSHR], anti-islet cells, anti CCP, Coombs test)			•							•	•	•	•	•	•	•	
Anti-BT063 antibodies			•							•	•	•	•	•	•	•	
Immunological status (HBV, HCV, HIV, tetanus, diphtheria, tuberculosis)		•								• ^a	•	•	•	•	•	• ^a	

Study 990 Part I and II		Visit	V1	V2	V3	V4	V5	V6	V7	V8	V9	V10	V11	V12	V13	V14	
Assessments	Phase	Screening	Baseline	Treatment												EoT	Follow-up
EBV and CMV serology	•	• ^a											•			• ^a	
Pregnancy test (in women of childbearing potential) or FSH assessment (in women not of childbearing potential) ^b	•	•						•			•						
Concomitant medications		•	•	•	•	•	•	•	•	•	•	•	•	•	•		
Efficacy Assessments																	
SLEDAI-2K score	•			•													
CLASI Activity score	•			•													
BILAG score	•			•													
Tender joint count, swollen joint count	•			•													
Physician's Global Assessment of Disease Activity	•			•													
Subject Reported Outcomes (SF-36v2, FACIT-F)	•			•				•			•		•				
ECLAM	•							•			•		•				
PK Assessments																	
BT063 serum level ^d		••	•	••	••	••	••	••	••	••	••	••	•g	•	•		
PD Assessments																	
T- and B-lymphocytes (CD3, CD4, CD8, CD19, CD20, CD27, CD38, CD69, CD62L, HLA DR,		•											•			•	

Assessments	Phase	Screening	Baseline	Treatment												EoT	Follow-up				
				V1				V2				V3				V4					
				Week	W -4 to -1	W 0	W 1	W 1	W 2	W 4	W 6	W 8	W 10	W 12	W 13	W 14	W 16	W 18	W 20	W 22	W 24
CD45RA)																					
Complement activity CH50, C3, and C4		•							•								•	•	•	•	•
ESR and CRP		•							•								•	•	•	•	•
Cytokines (IL-1 β , IL-2, IL-4, IL-5, IL-6, IL-8, IL-10, TNF- α , IFN- γ)		•							•								•	•	•	•	•
Immunological parameters		•															•	•	•	•	•
Immunoglobulins (IgG, IgM, IgA, IgE)		•															•	•	•	•	•
Free IL-10 ^h		••							••								•	•	•	•	•
Biomarker		•								•							•	•	•	•	•
IMP																					
Randomization																					
Administration of study drug																					

Abbreviations: ALT = alanine aminotransferase; AP = alkaline phosphatase; AST = aspartate aminotransferase; BILAG = British Isles Lupus Assessment Group; CCP = cyclic citrullinated peptide; CLASI = Cutaneous Lupus Erythematosus Disease Area and Sensitivity Index; CMV = cytomegalovirus; D = day; EBV = Epstein-Barr virus; ECG = electrocardiogram; ECLAM = European Consensus Lupus Activity Measurement; EoT = end of treatment; ESR = erythrocyte sedimentation rate; CRP = C-reactive protein; FACIT-F = Functional Assessment of Chronic Illness Therapy-Fatigue; FSH = follicle-stimulating hormone; fT3 = free triiodothyronine; fT4 = free thyroxine; GGT = gamma glutamyl transferase; HBV = hepatitis b virus; HBC = hepatitis C virus; IMP = investigational medicinal product; LDH = lactate dehydrogenase; PD = pharmacodynamic; PK = pharmacokinetic; RBC = red blood cells; SLEDAI-2K = Systemic Lupus Erythematosus Disease Activity Index 2000; V = visit; W = week; WBC = white blood cells

- Retention sample only.
- Urine pregnancy test at all scheduled visits; FSH at screening only.
- Availability of a signed and dated informed consent is to be confirmed baseline.
- Sampling for BT063 serum levels before and after IMP infusion at each dosing visit.

e) Potential subjects will be notified prior to V1 to fast for at least 12 hours before the scheduled visit. Laboratory assessments include: haematology (haematocrit, haemoglobin, RBC, WBC, differential WBC, platelets), coagulation (fibrinogen, prothrombin time, partial thromboplastin time), clinical chemistry (ALT, AST, GGT, AP, LDH, lipase, bilirubin, total protein, albumin, creatinine, urea, sodium, chloride, potassium, calcium), urinalysis: dipstick (pH, qualitative for blood, leucocytes, protein, glucose, ketone bodies, bilirubin, urobilinogen, nitrates, specific gravity) and microscopy, and faecal occult blood test. Faecal occult blood will be assessed at V2, V6 and V12 only.

In addition, the following will be assessed at Visits V1, V2, and V12 only: thyroid stimulating hormone, fT3 and fT4, fasting glucose, fasting triglycerides, fasting cholesterol, fasting high-density lipoprotein, and fasting low-density lipoprotein.

f) Subjects should not eat or drink anything except water for 12 hours before the fasting glucose and fasting lipid tests at Visits V1, V2, and V12.

g) BT063 serum level sampling at Visit 11 at least 5 days after last dosing (Visit 10).

h) Free IL-10 sampling before and after IMP infusion at V2, V5 and V6; at all other visits before IMP infusion only.

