represented by the area under the concentration-time curve (AUC) and C_{max} were approximately dose proportional. The mean BT063 half-life ranged between 20 days and 26 days. A transient mild IL-10 dose-dependent increase was observed at doses above 7.5 mg. This increase might be caused by prolonged circulation of IL-10 neutralized by BT063. Apart from IL-10, no BT063-related effects on cytokine levels and lymphocyte values were observed during Study 977.

Cynomolgus monkey is regarded as a relevant animal model due to cross reaction of BT063 with monkey IL-10. In a multiple dose toxicity study (Study BE-092-43/00), cynomolgus monkeys received 7 fortnightly doses of 1, 7, or 50 mg/kg BT063 by IV for a total of 13 weeks. The low dose level of 1 mg/kg is comparable to a human equivalent dose of ~ 330 μ g/kg, resulting in a total human dose of 20 mg (60 kg body weight) assuming equivalency on the basis of mg/m². For the high level dose of 50 mg/kg, the equivalent total human dose would be 1000 mg/kg. No clinical signs considered to be related to BT063 were observed up to the highest dose administered, except minimal transient platelet rises observed at 50 mg/kg. No signs of mouth ulcers were evident. Also no difference between male and female cynomolgus monkeys could be detected.

Finally, the total exposure (AUC) and maximal concentration over a 13-week treatment with the highest dose in monkey were several fold (>10-fold) above those predicted for humans treated with a dose up to 200 mg biweekly.

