10. Received the following medications: 
 • Rituximab within the last 48 weeks before screening • Belimumab within the last 12 weeks before screening • IV immunoglobulin within the last 12 weeks before screening • Intramuscular (IM) or intra-articular glucocorticosteroids within the last 4 weeks before screening • IV cyclophosphamide within the last 6 months before screening • IV glucocorticosteroids (pulse therapy) within the last 6 months before screening 	Medical	•	
11. Participation in another clinical study in the 90 days prior to baseline or within 5 half-lives of the investigated compound, whichever is longer; Participation in another clinical study during this study and/or previous participation in this study	Medical		•

Exclusion Criteria	Rationale	Screening	Baseline
12. Pregnant or nursing women or women who intend to become pregnant	Medical	•	•
13. Men or women not will to use effective contraception excluding women not of childbearing potential (Subjects who are sexually active women of childbearing potential or sexually active men who are not practicing 2 different methods of birth control with their partner during the study and for 4 months after the last dose of IMP or who will not remain abstinent during the study and for 4 months after the last dose. If using birth control, each couple must use 2 of the following precautions: vasectomy, tubal ligation, vaginal diaphragm, intrauterine device, birth control pill, birth control implant, birth control depot injections, condom, or sponge with spermicide. Women who are not of childbearing potential include those who are at least 1 year post-menopausal confirmed by follicle-stimulating hormone [FSH] levels or women who are surgically sterile.)	Medical	•	•
14. Known intolerance to immunoglobulins or comparable substances (e.g., significant vaccination reaction)	Medical	•	
15. Known intolerance to proteins of human origin	Medical	•	
16. Employee or direct relative of an employee of the CRO, the study site, or Biostest	Administrative	•	•
17. History of clinically significant drug or alcohol abuse within the last 12 months	Medical	•	
18. Any other significant acute or chronic illness or laboratory abnormality, which, in the opinion of the investigator, might compromise the safety of the subject or influence the outcome of the study and its objectives.	Medical	•	

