13.1.1 Screening - Visit 1, Days -28 to -7 (Week -4 to -1)

The following procedures are to be completed during the screening period at time points designated on the Flowchart of the Study ([Section 3](#)).

- Provide informed consent and request ICF signature
- Record demographic data including sex, age, race, and ethnicity
- Record medical/surgical history (including any risk factors)
- Record previous and current medications as well as history of vaccinations
- Verify eligibility (inclusion/exclusion criteria)
- Complete full physical examination (including weight and height)
- Measure and record vital signs (pulse, blood pressure, and body temperature)
- Perform 12-lead ECG
- Draw blood for safety and eligibility laboratory assessments (haematology, coagulation, and clinical chemistry), auto-antibodies (ANA, anti-dsDNA, thyroid gland [TPO and TSHR], anti-islet cells, anti-CCP, and Coombs test); immunological status (HBV, HCV, HIV, tetanus, diphtheria, tuberculosis); and EBV and CMV serology
- Draw additional blood for the following tests: thyroid-stimulating hormone (TSH), fT3, fT4, fasting glucose, fasting triglycerides, fasting cholesterol, fasting high-density lipoprotein, and fasting low-density lipoprotein (fasting must be for at least 12 hours)

- Obtain sample for urinalysis
- Urine pregnancy test for women of childbearing potential, FSH assessment for women not of childbearing potential
- Perform and record the following assessments:
 - SLEDAI-2K
 - CLASI Activity score
 - BILAG score
 - Tender joint count and swollen joint count
 - Physician's Global Assessment of Disease Activity
- Draw blood for PD assessment: complement activity (CH50, C3, and C4)

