13.1.2 Baseline – Visit 2, Day 0 (Week 0)

Baseline procedures will be performed on Day 0, the first day of IMP administration. The following procedures are to be completed at time points designated on the Flowchart of the Study ([Section 3](#)).

- Confirm that the ICF has been signed
- Confirm eligibility (inclusion/exclusion criteria)
- Record AEs
- Perform full physical examination
- Measure and record vital signs (pulse, blood pressure, and body temperature)
- Draw blood for safety laboratory assessments (haematology, coagulation, and clinical chemistry), auto-antibodies (ANA, anti-dsDNA, thyroid gland [TPO and TSHR], anti-islet cells, anti-CCP, and Coombs test), and anti-BT063 antibodies; as well as retention samples for immunological status and EBV and CMV serology
- Draw blood for the following additional tests: TSH, fT3, fT4, fasting glucose, fasting triglycerides, fasting cholesterol, fasting high-density lipoprotein, and fasting low-density lipoprotein (fasting must be for at least 12 hours)
- Obtain samples for urinalysis and faecal occult blood test
- Urine pregnancy test for women of childbearing potential
- Record concomitant medications
- Perform and record the following assessments:
 - Subject Reported Outcomes: FACIT-F and SF-36v2
 - SLEDAI-2K
 - CLASI Activity score
 - BILAG score
 - Tender joint count and swollen joint count
 - Physician's Global Assessment of Disease Activity
 - ECLAM
- Draw blood for PD assessments: T- and B-lymphocytes (CD3, CD4, CD8, CD19, CD20, CD27, CD38, CD69, CD62L, HLA DR, CD45RA), complement activity, ESR and CRP, cytokines (IL-1 β , IL-2, IL-4, IL-5, IL-6, IL-8, IL-10, TNF- α , and

INF- γ), immunological parameters, immunoglobulins (IgG, IgM, IgA, and IgE), and biomarkers

- Draw blood before IMP administration for serum BT063 level and Free IL-10
- Randomize subject and administer IMP
- Draw blood after IMP administration for serum BT063 level and Free IL-10
- Ask the subject to stay at the investigational site for at least an additional 2 hours and monitor for a type I hypersensitivity reaction

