13.1.13 Follow-up – Visit 13, Day 140±7 (Week 20)

The following procedures will be completed at the first Follow-up Visit at the times designated on the Flowchart of the Study ([Section 3](#)).

- Record AEs
- Perform targeted physical examination
- Measure and record vital signs (pulse, blood pressure, and body temperature)
- Draw blood for safety laboratory assessments (haematology, coagulation, and clinical chemistry), auto-antibodies (ANA, anti-dsDNA, thyroid gland [TPO and TSHR], anti-islet cells, anti-CCP, and Coombs test), and anti-BT063 antibodies
- Obtain sample for urinalysis
- Record concomitant medications
- Perform and record the following assessments:
 - Subject Reported Outcomes: FACIT-F and SF-36v2
 - SLEDAI-2K
 - CLASI Activity score
 - BILAG score
 - Tender joint count and swollen joint count
 - Physician's Global Assessment of Disease Activity
 - ECLAM
- Draw blood for PK and PD assessments: serum level of BT063, complement activity, ESR and CRP, Free IL-10.

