13.5.2 Foreseeable Risk and Discomfort Related to BT063

13.5.2.1 *Potential risks*

- Uncertain effect on the mucous membrane of the gastrointestinal tract (GI)
- Hypersensitivity reactions
- Interactions with other drugs
- Interaction with live vaccines or induction of immune system overreactions in vaccinated subjects
- Infections

13.5.2.2 *Identified risks*

Based on the results of the completed Phase I study in healthy subjects the following risks were classified as identified for BT063:

- Mouth ulcers/aphthous stomatitis

13.5.2.3 *Important missing information*

- Lack of knowledge about potential influence on pregnant women and embryonic development

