Pregnancy Reporting: Each pregnancy that starts during the study must be reported by the investigator to [REDACTED] Drug Safety Department within 24 hours of the investigator's knowledge of the pregnancy by using the SAE Form. Any adverse outcome of the pregnancy must be recorded and notified on the "Drug Exposure via Parent Report Form". The investigator should make any reasonable effort to follow any pregnancy until birth of the child.

Overdose (as defined in [Section 11.1.4](#)) needs to be reported to [REDACTED] Drug Safety Department following the criteria for SAE reporting.

If additional information is required by the [REDACTED] Drug Safety department, then as a representative of the Sponsor [REDACTED] must be granted access to the medical records.

After subject's last study visit:

The investigator records and forwards to the Sponsor all SAEs that she or he becomes aware of and she or he considers related to the IMP.

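### Scheduled pregnancy testing ends 14 days after the last dose, leaving most of the protocol's 4-month contraception period untested, and flowchart footnote b does not say clearly which visits carry the test

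*Protocol*

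**What the plan says.** The visit lists in Section 13.1 of the protocol place a urine pregnancy test at six of the 14 visits:

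- Screening (Visit 1): "Urine pregnancy test for women of childbearing potential, FSH assessment for women not of childbearing potential".
- Baseline (Visit 2, Day 0): "Urine pregnancy test for women of childbearing potential". Equivalent lines stand at Visit 6 (Day 28), Visit 8 (Day 56), Visit 10 (Day 84, the last dose) and Visit 12 (Day 98, End of Treatment).
- Follow-up Visit 13 (Day 140) lists "Obtain sample for urinalysis" but no pregnancy test. The list for Visit 14 (Day 196) has the same urinalysis line and again no pregnancy test.

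Footnote b to the flowchart in Section 3 reads "Urine pregnancy test at all scheduled visits; FSH at screening only".

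Three other places bear on the follow-up period. Exclusion criterion 13 in Section 12.3 asks for two methods of birth control, or abstinence, "during the study and for 4 months after the last dose of IMP". Section 13.5.2.3 has a single entry under missing information: "Lack of knowledge about potential influence on pregnant women and embryonic development". Section 11.1.3 reports from the single-dose study in healthy subjects that "The mean BT063 half-life ranged between 20 days and 26 days". On reporting, Section 14.3.2.1 states "Each pregnancy that starts during the study must be reported", within 24 hours of the investigator learning of it.

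**The concern.** The protocol treats the months after the last dose as a time when conception should be avoided, and it admits that it does not know what BT063 does to a pregnancy. During treatment it tests every four weeks. Once dosing stops, it tests once more at two weeks and then not again, while the antibody is still being cleared and while serum BT063 is still sampled on Days 140 and 196 (Section 14.2.3.2).

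At stake is the capture of safety information. The benefit-risk summary in Section 13.5.4 relies on mitigation of, among other things, the important missing information. A conception in follow-up reaches the database only if the woman knows of it and says so, and an unrecognised early pregnancy or loss is the kind most easily overlooked. In a small study with repeated dosing in patients, each exposed pregnancy would be informative.

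The footnote adds a practical risk: sites can read it in different ways and so test at different visits.

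**Working it through.** The plan states no figure to reproduce. The check compares the visit lists and then uses simple date and decay arithmetic. The flowchart row itself is not relied on, because its layout did not survive text extraction.

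**1. Visit lists against footnote b.**

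- Test listed: Visits 1, 2, 6, 8, 10, 12 (6 of 14).
- Test not listed: Visits 3, 4, 5, 7, 9, 11, 13, 14 (8 of 14).

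Taken literally, the footnote conflicts with all eight visits in the second row. Taken as referring to the visits marked in its own row of the flowchart, it need conflict with none. Under the second reading, testing as listed in Section 13.1 still ends at Day 98.

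**2. Length of the post-dose contraception period.** The synopsis and Section 9 describe post-dose follow-up as 4 months. Section 13.2 gives the same span as 16 weeks. On that usage, 16 × 7 = 112 days, and Day 84 + 112 = Day 196, the nominal day of the last visit.

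**3. Share without a scheduled test.** The last test is on Day 98, which is 98 − 84 = 14 days after the last dose. The remainder is 112 − 14 = 98 days, and 98/112 = 0.875, about 88%. From baseline to the last dose, the interval between listed tests is 28 days (Days 0, 28, 56, 84).

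**4. Drug remaining.** Fraction of the level after the last dose = 0.5^(t / half-life), with t counted from Day 84 and the half-lives of 20 and 26 days from Section 11.1.3:

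| Day | t (days) | half-life 20 d | half-life 26 d |
|---|---|---|---|
| 98 (Visit 12, last test) | 14 | 0.616 | 0.689 |
| 140 (Visit 13) | 56 | 0.144 | 0.2247 |
| 196 (Visit 14) | 112 | 0.021 | 0.050 |

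So about 62 to 69% remains at the last test, 14 to 22% at Day 140 and 2 to 5% at Day 196. The formula assumes one-phase elimination, and the half-lives come from single doses in healthy subjects, so these figures are illustrative.

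**5. Women exposed.** BT063 goes to 12 subjects in each part, 24 of 36 in all (Section 9). Section 12.1.1 expects about 90% women: 0.90 × 24 = 21.6, about 22. This assumes that Part II goes ahead and that the sex ratio is the same in both arms. If only Part I runs, 0.90 × 12 = 10.8, about 11. The number of childbearing potential cannot be derived from the protocol.

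**6. Effect of adding tests at Visits 13 and 14.** The longest interval without a test in follow-up falls from 98 days to 56 (Day 140 to Day 196), and the last test falls at the nominal end of the 16-week period.

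**The case against.** The best defence is that safeguards already exist. Two-method contraception or abstinence is required. Women are seen, examined and asked about their health at Visits 13 and 14. Any pregnancy must be recorded, reported promptly and followed to birth where possible, and a congenital anomaly counts as a serious adverse event. After the last dose a test can no longer prevent dosing during a pregnancy; it only helps to record one. This stands in part: detection in follow-up is not absent. But the reporting duty starts only when the investigator knows, and Section 14.1.2.1 calls for non-leading questions, so detection depends on what the subject knows and volunteers. That does not replace a scheduled test.

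A second defence is that footnote b means each visit marked in its row, with FSH at screening alone. This is a reasonable reading and may be the intended one. Nearby footnotes do name their visits when they limit a test, which leaves the wording open. A reader might infer a plain contradiction confined to the two follow-up visits. The text does not support that: the literal reading also conflicts with six visits during treatment, and the narrower reading removes the conflict altogether.

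A reader might also convert 4 months into about 122 days, place the end of contraception near Day 206, and conclude that it outlasts both the last visit and pregnancy reporting. The protocol does not support this either, because it uses 4 months for its own 16-week post-dose period. What is left is at most a rounding ambiguity of about 10 days.

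**Conclusion.** The gap is real on either reading of footnote b. Testing stops at Day 98 with about 88% of the 16-week post-dose contraception period still to run, more than half of the last-dose level still present under the illustrative decay, and urine already being collected at both later visits.

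The supported conclusion is that pregnancies exposed to BT063 can go undetected in follow-up. It would be too strong to say that they will be missed, since subjects may report them, or that added tests would catch every one, since a loss between visits could still escape. It would also be too strong to count all of the roughly 32 women expected among 36 subjects (0.90 × 36 = 32.4) as exposed, because a third of subjects receive placebo; about 22 is the relevant figure, and fewer will be of childbearing potential.

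The result rests on the Section 13.1 lists being the operative schedule and on 4 months meaning 16 weeks. No efficacy endpoint or planned analysis changes. The point concerns the completeness of safety data and one unclear footnote, and it is worth correcting because the correction is so cheap.

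**What to change.** 1. Reword footnote b so that it names the visits at which the urine test is done, and make it agree with the Section 13.1 lists and the flowchart row. This settles the footnote for the treatment visits as well as for follow-up.
2. Add the urine pregnancy test for women of childbearing potential to the lists for Visit 13 (Section 13.1.13) and Visit 14 (Section 13.1.14), run on the urine already collected there.

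The contraception period, the dosing and the pregnancy-reporting sentence can stay as they are. The cost is one footnote, two lines of text and the matching flowchart marks, two strips per woman of childbearing potential, and a little more pregnancy follow-up work if a test is positive. No extra visit or blood draw is needed.
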